As shown in Figure 3, proposed is a 2X2 factorial randomized clinical effectiveness trial testing the effects of combining CM as an adjunct to state-of-the-art, evidence-based CBT (CBT + CM vs. CBT only) and the effects of a single, long-term incentive for bioverified abstinence/no heavy drinking at 6-months follow-up (Long Term Incentive vs. No Incentive). All patients will be referred to standard aftercare and encouraged to participate in 12-step programs following the intervention. Use of aftercare and other health care utilization will be collected based on objective measures (VA electronic medical record) and participant report. Health-related quality of life will be collected at each follow-up. The primary endpoint (AIM 1) will be number of heavy drinking days in the past 30 days at the 6-month follow-up. Cost effectiveness analysis (AIM 2) will be performed using quality-adjusted life years (QALY) as the outcome. The utility of a long-term incentive (AIM 3) will be tested by examining use of aftercare and other alcohol-related treatment and heavy drinking days in the past 30 days at the 6 and 12-month follow-ups.

D.2. Patient Identification, Eligibility, and Recruitment

Patients will be identified from the Durham VA Health Care System (DVAHCS) using the hospital's computerized medical record. Records will be screened for AUD. After mailing introductory materials with an opt-out number, we will contact those who do not opt out via telephone to explain the study and recruit them for participation. If necessary, in order to reach female veterans, we can oversample women for the screening mailouts.

Figure 3. Trial Design

We will also utilize reactive recruitment methods as needed to reach potentially eligible veterans. For example, we will seek referrals from the DVAHCS Substance Use Disorders Clinic. In order to reach female veterans, we will seek referrals from the Women's Health Clinic. In addition, we will post IRB-approved flyers and brochures throughout the DVAHCS catchment area, especially in clinic areas and Vet Centers. In addition, we will post, if necessary, flyers and brochures in the community, in local restaurants, laundromats, university student centers, etc. We will also use online classified advertisements such as Craigslist.com to reach potential participants.

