Cost and Effectiveness Measurement. Our primary cost effectiveness outcome measure will be the incremental cost-effectiveness ratio (ICER), with costs as the numerator and effectiveness as measured by QALYs as the denominator. Costs will include: intervention delivery costs, participant time costs and health care costs as described above. The QALY is a standardized effectiveness measure, based on the EuroQol (EQ-5D5L), that allows for the comparison of the value of a particular intervention to a broad range of other potential health care investments. Differences in reduction in heavy drinking days and secondary drinking outcomes (e.g., abstinence) among veterans in the mCM+CBT and the CBT comparison group will allow us to identify changes in the QALY effectiveness measure across groups. To estimate the QALYs, we will employ the methods and estimates developed by Barbosa and colleagues (2010), who used a Markov model to assign utility weights to a range of drinking patterns for medical morbidity and mortality, adjusted for health-related quality of life. Incremental costs and effectiveness of mCM+CBT will be compared to those of the CBT comparison group.

D.7. Optional Study Procedure

One of our study therapists, [name], is seeking licensure as a Licensed Professional Counselor, and as part of her supervision, needs to provide video recordings of therapy sessions to her supervisor, [name], MS, LPCS for review. Data will be shared with [name] as view only in a Duke Box folder to which only [name], [name], and [name] have access. Data will be shared in accordance with a data agreement facilitated by Duke’s Office of Research Contracts, and signed by [name] and [name]. This study procedure is fully optional, and is indicated as such during the informed consent process.

D.8. Measures

Participants will complete measures at primary assessment time points (baseline, post-treatment, 6 months post-quit date, and 12 months post-quit date), as well as reporting on alcohol at each CBT session. Follow-ups will be completed in-person.

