We plan to ask participants to report both gender and biological sex so that we can evaluate the role of biological sex on study outcomes. The association between sex and outcomes will be evaluated for all three aims. We will conduct sensitivity analyses to determine how variability in demographic/baseline variables influence estimates of treatment effects by analyzing and reporting the effects of randomization on males and females separately.

Multilevel modeling (MLM) will be used to analyze primary treatment outcomes (i.e., number of heavy drinking days; abstinence outcomes). MLM is appropriate for analyzing repeated-measures data; however, unlike ANOVA, MLM can accommodate data missing at random (Searle, Casella, & McCulloch, 1992). Because MLM takes into account the shared variance among observations within a given person, it can be used to leverage repeated measurements of alcohol use to enhance statistical power.

Although we do not anticipate much missing baseline data, we do anticipate missing values at post-treatment and each of the 6- and 12-month follow-ups due to attrition. Given evidence that maximum likelihood (ML) and multiple imputation (MI) provide the least biased results in comparison to last observation carried forward and worst-case scenario (i.e., missing=relapsed) in alcohol clinical trials under varying missing data assumptions (Hallgren & Witkiewitz, 2013), both approaches will be used here. MLM uses ML estimation; thus, missing values result in casewise—but not listwise—deletion. Consequently, participants with missing data will still be included in the analyses; estimates based on them will simply have a greater level of uncertainty. MI will be used to impute missing data using baseline demographic, clinical, and drinking measures. Regression parameter estimates will be computed for each imputation dataset and then pooled using Rubin's rules (Rubin, 1976). Sensitivity analyses will be conducted to determine how modeled treatment effects may vary by missing-data approach.

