Aim 2: To examine the hypothesis that mCM paired with CBT for SUD will be more cost effective over the lifetime than CBT alone, cost-effectiveness analysis (CEA) will be performed using the incremental cost-effectiveness ratio (ICER), with costs as the numerator and effectiveness as measured by quality-adjusted life years (QALY) as the denominator. QALYs incorporate changes in quality of life (morbidity) using a set of values, one for each possible health state, reflecting the relative desirability of the health state (Drummond et al., 2009). Quality of life ratings, or utilities, will be derived from a prior study of the utility of different drinking states that used the standard gamble technique in a community/clinic sample of 200 individuals (Kraemer et al., 2005). The mean utility values (and standard deviations) calculated for each state were as follows: abstinent 0.93 (0.15), moderate drinking 0.88 (0.22), at-risk drinking 0.82 (0.27), meeting criteria for mild AUD 0.75 (0.29), meeting criteria for severe AUD 0.67 (0.29), and in recovery from alcohol dependence 0.83 (0.24). QALY change will be calculated based on change from baseline to 12-month drinking status. Prior to CEA, CBT alone will be assessed for dominance to determine whether it is both less costly and more effective than combined mCM and CBT. In the absence of dominance, an incremental cost-effectiveness ratio (ICER) will be computed to estimate the additional cost required to achieve one additional QALY. Specifically, the ICER combines the costs of the treatments with the QALY changes, using the cost in the mCM group over and above the control, divided by the incremental QALYs in the mCM group over and above the control. Given likely skewed economic data, nonparametric bootstrap resampling will be used to test the sensitivity of the calculated ICERs and cost-acceptability curves estimated to assess the probability that the mCM intervention is cost-effective at thresholds up to \$50,000 or \$100,000 per QALY (Willan & Briggs, 2006). Numerous sensitivity analyses will be conducted to evaluate the robustness of these results given varying estimates of abstinence rates, relapse to any heavy drinking, mortality rates, and long-term costs of sustained alcohol use. Cost-effectiveness analysis will be conducted if the primary outcome is significant; otherwise, a cost minimization analysis will be conducted.

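### A non-significant drinking result replaces the cost-effectiveness analysis with cost minimisation, although the plan has no basis for assuming equal effects

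*Combined protocol and SAP*

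**What the plan says.** The rule is the last sentence of the Aim 2 paragraph in section F: "Cost-effectiveness analysis will be conducted if the primary outcome is significant; otherwise, a cost minimization analysis will be conducted".

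Other places in the combined protocol and SAP bear on it:

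- **Title and section A (Specific Aims).** Cost effectiveness is in the title and is part of the stated primary goal. Aim 2 is to evaluate it in QALYs, with no condition.
- **D.1 (Study Design).** "Cost effectiveness analysis (AIM 2) will be performed using quality-adjusted life years (QALY) as the outcome". On the clinical side: "The primary endpoint (AIM 1) will be number of heavy drinking days in the past 30 days at the 6-month follow-up".
- **D.6 (Cost Effectiveness).** The ICER is named as the primary cost-effectiveness measure, again without condition. Costs cover intervention delivery, participant time and health care.
- **Section F, multilevel modelling paragraph.** Heavy drinking days and abstinence are both listed as primary treatment outcomes.
- **Section F, Aim 2, before the rule.** The paragraph opens by saying the ICER analysis will be performed. On effects it says "QALY change will be calculated based on change from baseline to 12-month drinking status". It plans bootstrap resampling and acceptability curves at thresholds of $50,000 and $100,000 per QALY. It also plans a dominance check in one direction: "CBT alone will be assessed for dominance to determine whether it is both less costly and more effective".

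No section gives an equivalence or non-inferiority margin, hypothesis or test. Section F states no significance level.

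**The concern.** Cost minimisation is valid when effects are known, or have been shown, to be equal. Here the only trigger is failure to reject in a superiority test, so lack of evidence for a difference is treated as evidence of none.

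The trigger also differs from the quantity it controls. The primary endpoint is heavy drinking days at 6 months, while the ICER denominator rests on drinking status at 12 months. Because section F also calls abstinence primary, the plan does not say what happens if one outcome is significant and the other is not.

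At stake is the main measure of an aim named in the title. After a non-significant result, the analysis becomes a costs-only comparison, and the plan no longer provides for the QALY difference or its joint uncertainty with cost. Which arm is cheaper overall cannot be known in advance, because health care and participant time are counted.

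**Working it through.** **1. Is the rule consistent with the rest of the plan?** Specific Aims, D.1, D.6 and the opening of the Aim 2 paragraph state the QALY or ICER analysis without condition. Only the final sentence of that paragraph adds one. The planned bootstrap and acceptability curves do not need a significant clinical effect, and they are most useful when the effect is uncertain.

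**2. Reproducing the plan's power figures.** Inputs from the power paragraph of section F: 140 participants, 3 observations each, ICC 0.20, and 119, 101 and 86 remaining at the three visits. With m observations per person, the effective sample size is the sum of n·m / (1 + (m − 1)·ICC).

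- No attrition: 140 × 3 / 1.4 = 300, as stated.
- With attrition: 86 × 3/1.4 + 15 × 2/1.2 + 18 = 227.3, stated as 227.
- Assuming two-sided 0.05 and 1:1 allocation, power at d = 0.43 with 227 is 0.8996, stated as 90%. One-sided 0.05 would give 0.945, so two-sided fits.

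**3. How often would a real effect be sent to cost minimisation?** By the normal approximation, the standard error of d is 2/√N. The miss probability is 1 − [Φ(d√N/2 − 1.96) + Φ(−d√N/2 − 1.96)], without covariate adjustment. The value d = 0.30 is my assumption; 0.43 and 0.92 are in the plan. The rows for 140 and 101 count each participant once, because the primary endpoint is read at a single visit.

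| N | d = 0.30 | d = 0.43 | d = 0.92 |
|---|---|---|---|
| 227 (plan's effective size) | 38% | 10% | under 1% |
| 140 (all randomised) | 57% | 28% | under 1% |
| 101 (seen at 6 months) | 67% | 42% | under 1% |

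Baseline adjustment helps. With an assumed correlation of 0.5, d = 0.43 becomes 0.43/√0.75 = 0.497, and the miss rate with 101 falls to about 30%.

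**4. What does a non-significant result leave open?** The 95% half-width is 1.96 × 2/√N.

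| N | Half-width | Upper limit when just non-significant |
|---|---|---|
| 227 | 0.26 | 0.52 |
| 140 | 0.33 | 0.66 |
| 101 | 0.39 | 0.78 |

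An estimate of exactly zero would exclude 0.43. The interval includes 0.43 once the estimate reaches 0.43 − 0.26 = 0.17 (N = 227) or 0.43 − 0.39 = 0.04 (N = 101).

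**5. Could the trial show equivalence instead?** I used two one-sided tests at 0.05 with a true difference of zero and illustrative margins. At a margin of 0.30, power is 46% (N = 227) or 0% (N = 101). At 0.43 it is 89% or 39%.

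**6. Can a small effect matter economically?** This is for scale only and counts incentives alone. At $50,000 per QALY, $611 (the expected incentive total under perfect adherence) breaks even at 611/50,000 = 0.012 QALY. With the utilities in the Aim 2 paragraph, and the full gap held for one year:

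- severe AUD to abstinent, 0.93 − 0.67 = 0.26: about 5 per 100 participants;
- severe AUD to recovery, 0.83 − 0.67 = 0.16: about 8 per 100;
- at-risk to moderate drinking, 0.88 − 0.82 = 0.06: about 20 per 100;
- moderate drinking to abstinent, 0.93 − 0.88 = 0.05: about 24 per 100.

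If the change builds up linearly over the year, the gain halves and these counts double. At $100,000 per QALY they halve.

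**The case against.** The strongest reply has four parts.

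- **A specific rule can qualify general text.** The closing sentence of Aim 2 may be read as a condition on the earlier statements. That softens the conflict, but nothing in Specific Aims, D.1 or D.6 signals a condition, and on this reading the rule still lacks an equivalence basis.
- **The trigger has a natural reading.** The rule speaks of one primary outcome, and D.1 names one. This is fair. The looseness comes from the second list in section F and is the lesser point.
- **The miss rates depend on pessimistic inputs.** The 0.43 is the smallest effect the plan aims to detect, not the one it expects; 0.30 is not in the plan; and the rows for 140 and 101 set aside the repeated-measures model. On the plan's own figures, 10% is ordinary type II error. All of this is correct. The rates show how often the rule could misfire and do not carry the argument.
- **The break-even is fragile.** It omits other costs, and the Aim 2 paragraph speaks of lifetime cost effectiveness, for which a one-year break-even does not apply. It serves only to show scale.

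It is also true that the rule is openly pre-specified, leaves the primary clinical estimate untouched and loses no data, so an ICER could still be computed outside it. None of this makes a non-significant superiority test evidence of equal effects.

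**Conclusion.** The concern holds, and the sentence is wrong as written. The conclusion rests on the text: cost minimisation needs equal effects, the plan has no means of showing them, and four other statements promise the analysis that the rule can remove.

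The size depends on the true effect. Misfires would be rare at the cited prior effect. At the plan's own detectable effect they range from 10% to 42%, according to whether the effective sample size or the unadjusted 6-month count is used. Two-sided 0.05 and 1:1 allocation are assumed throughout. Because the rule can displace the main measure of a titular aim, it must be corrected.

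**What to change.** Delete the last sentence of the Aim 2 paragraph and replace it with: *The cost-effectiveness analysis (incremental cost, incremental QALYs, bootstrap and acceptability curve) will be carried out whatever the result of the primary outcome test.* Specific Aims, D.1 and D.6 then need no change on this point. The amendment should be made before results by arm are seen, so that the choice cannot appear driven by the outcome.

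If cost minimisation is kept, allow it only after equivalence is shown against a pre-specified margin, and name the effect to which the margin applies. That option is weak at this sample size unless the margin is wide (step 5 of the working).

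Two optional additions are to report net monetary benefit at $50,000 and $100,000 per QALY from the same bootstrap, and to check dominance in both directions before reporting an ICER.

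The cost is one sentence and slightly more analysis work. Costs and outcomes are collected regardless, so no new data are needed.

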Our long-term goal is to implement cost-effective treatments that reduce the morbidity and mortality associated with alcohol and substance misuse. VA has widely implemented evidence-based cognitive-behavioral therapy (CBT) for treatment of substance abuse disorders (Karlin & Cross, 2014). The primary goal of the current study is to evaluate the clinical effectiveness and cost effectiveness of CM as an adjunct to CBT for AUD. The trial will also explore the potential utility of a long-term abstinence incentive on treatment utilization and alcohol outcomes. We plan to conduct a comparative effectiveness trial with a 2 x 2 factorial design in which 140 veterans with AUD will be proactively recruited and randomized to receive either CM as an adjunct to state-of-the-art evidence-based CBT, or receive CBT alone; and to one of two long-term incentive conditions (i.e., receipt of a monetary incentive for abstinence/low-risk drinking at 6-months vs. no incentive). Specific aims include:

AIM 1: To evaluate the effectiveness of mobile contingency management, as an augment to evidence-based CBT for AUD, on (1) treatment engagement and retention, and (2) reduction in heavy drinking days and abstinence from alcohol at post-treatment, 6-month and 12-month follow-ups.

Hypothesis 1a: Mobile contingency management for AUD will be associated with greater treatment engagement and treatment completion.

Hypothesis 1b: Mobile contingency management for AUD will be associated with decreased self-reported heavy drinking days and increased rates of abstinence from alcohol at each follow-up.

AIM 2: To evaluate the cost effectiveness of CM as an adjunct to evidence-based CBT for SUD in quality adjusted life years (QALY).

Hypothesis 2: CM paired with CBT will result in greater cost-effectiveness compared to the CBT alone as measured by the incremental cost-effectiveness ratio.

AIM 3: To explore the effects of a long-term (six-month) abstinence incentive on (1) treatment utilization and (2) alcohol outcomes at the 6-month and 12-month follow-ups.

Hypothesis 3: A long-term abstinence incentive will (1) increase utilization of AUD aftercare and (2) be associated with reduced heavy drinking days and increased abstinence rates.

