Potential participants who discuss the study with study personnel will complete a brief phone screen to assess potential eligibility. Veterans who are potentially eligible will attend a screening session where they will complete diagnostic interviews, self-report measures, urine drug screen and alcohol breathalyzer to determine inclusion. Participants who screen in will be randomized at the first treatment session to one of two treatment conditions (CBT+mCM vs. CBT alone) and to one of two long term incentive conditions (abstinence incentive at 6 months vs. No incentive). Stratified permuted block randomization assignments will be performed using a computerized sequence generated by the study statistician before the study starts. The sequence will be password-protected so that only the statistician and other study staff who do not have patient contact will have access to the sequence. We will stratify on the presence of comorbid non-tobacco SUD.

D.4. Interventions

D.4.1. Cognitive-Behavioral Therapy for Substance Use Disorders

We will use the VA CBT for SUD protocol (DeMarce, Gnys, Raffa, & Karlin, 2014) to provide in-person treatment in both study arms. CBT will be provided by a therapist with at least a Master's degree in mental health (e.g., psychology, social work) who has reviewed CBT for SUD training materials. To prevent confounding from therapist effects, study therapists will treat cases in both study arms. CBT sessions will be weekly over 12 weeks as shown in Figure 3. Following the standard of care for AUDs, all participants will be referred to aftercare and encouraged to participate in 12-step programs following completion of the 12-session CBT intervention (Proctor & Herschman, 2014).

Figure 3. Timeline for Intervention and Follow-Ups

D.4.2. Mobile Contingency Management for AUD Procedures

As shown in Figure 3, participants will begin one week of practice mCM monitoring at session two of CBT so they can troubleshoot any difficulties they have using the app. The beginning of contingent reinforcement (i.e., the target quit date) is scheduled for the same date as session three of CBT (week 3), which will provide eight weeks of mCM before the end of CBT. Patients who attend all weekly appointments will have two sessions of CBT occurring after mCM ends to assist in preventing relapse when monetary reinforcement is removed.

Table 2. Virtual Scratch-Off Lottery Ticket Reinforcement Amounts				

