Videos bioverifying alcohol abstinence will be reviewed by study staff to verify the participant's identity and alcohol abstinence. Study staff will write notes to the participant through the app to provide feedback on how the bioverification results translate into virtual scratch-off lottery tickets (scratch-offs). At that point, participants will use the app to reveal the scratch-offs and find out what level of reinforcement they have received. At the beginning of each session of CM+CBT, therapists will review the essential elements of CM as indicated on the Contingency Management Competence Scale (Petry, 2010). Essential elements include feedback and review of how bioverification results resulted in reinforcement draws, discussion of the mean number draws that could be earned if the participant is bioverified abstinent over the upcoming week, praise of the participant's efforts toward abstinence, communication of confidence that efforts will yield future success, and general competence ratings. This portion of the session will be rated by an independent fidelity rater using the Contingency Management Competence Scale. Therapists will be trained on the essential elements of CM during a half-day training. The CM portion of CM+CBT sessions will be videorecorded and rated by an independent fidelity rater.

Participants will be asked not to initiate any new treatments for AUD during the study treatment period. Following the active treatment period, participants will be encouraged to become involved with local 12-step programs and other aftercare.

D.4.3 Long Term Incentive

Participants randomized to the long-term incentive condition will receive \$300 for self-reported and bioverified 30-day abstinence from heavy drinking at the follow-up scheduled for 6-months after the initial quit date. Bioverification will be based on PEth test.

D.5. Rationale for CM Parameters

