Aim 3: To examine the hypothesis that incentivizing long-term abstinence will increase AUD aftercare treatment utilization, enrollment in VA and/or non-VA alcohol treatment programs will be determined both in the first 6 months following randomization and the second 6 months leading up to the 12-month follow-up. Logistic MLM will be used to model treatment utilization during each of these intervals as a function of randomization to the long-term abstinence incentive, time, and the interaction between group and time. Randomization to CM will be covaried. Linear contrasts will be specified at each time point to examine the hypothesis that long-term incentives to promote abstinence will result in greater likelihood of AUD treatment utilization both prior to and following the 6-month incentive. To examine the hypothesis that long-term abstinence incentives will be associated with higher rates of self-reported abstinence and fewer heavy drinking days at 6 and 12 months, MLM analyses similar to those proposed for Aim 1 will be conducted. Specifically, logistic MLM will be used to model abstinence as a function of long-term incentive, time (categorized as end of treatment, 6 months, 12 months), and the interaction between incentive and time. Randomization to CM will be covaried. Linear contrasts will be specified at each time point to examine the hypothesis that a long-term incentive for abstinence will result in higher abstinence rates than no incentive at 6 and 12 months. A similar count-based model (e.g., Poisson, negative binomial) will be conducted to analyze number of days of heavy drinking (per 30

days). In addition to modeling the effects of long-term incentive, time, and the interaction between incentive and time, number of days of heavy drinking recorded at baseline and randomization to CM will be covaried. Linear contrasts will compare effects of the incentive at 6 and 12 months.

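### Aim 3's first aftercare window is anchored at randomisation: it ends about two weeks before the incentive visit, and 42–46% of it is study treatment

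*Combined protocol and SAP*

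**What the plan says.** Hypothesis 3 (Section A) is that "A long-term abstinence incentive will (1) increase utilization of AUD aftercare". To test it, Section F (Aim 3) determines enrolment in VA or non-VA alcohol programmes "in the first 6 months following randomization and the second 6 months leading up to the 12-month follow-up". A logistic multilevel model is fitted with incentive group, time and their interaction. The stated purpose of the contrasts is to test the incentive's effect on treatment use before and after the 6-month incentive.

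The plan uses two clocks:

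- **Randomisation.** Section D.3: "Participants who screen in will be randomized at the first treatment session to one of two treatment conditions". Section D.4.1: "CBT sessions will be weekly over 12 weeks as shown in Figure 3".
- **Quit date.** Section D.4.2 places it at CBT session 3. Section D.4.3 schedules the incentive visit six months after it, and Section D.8 times the 6- and 12-month assessments from it.

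On treatment outside the study, Section D.4.2 says: "Participants will be asked not to initiate any new treatments for AUD during the study treatment period". Sections D.1, D.4.1 and D.4.2 all place the encouragement towards aftercare after the intervention.

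**The concern.** Two features of the windows do not match the question Aim 3 asks.

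First, the dividing line between them is set on the randomisation clock, but the event it should mark, the incentive visit, is set on the quit-date clock. A contrast described as before versus after the incentive is then divided at a different date.

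Second, the first window opens on the day study CBT starts. For about its first 12 weeks participants are asked not to begin other AUD treatment and have not yet reached the stage at which aftercare is encouraged. The outcome is binary, so a person who enrols elsewhere in that period is already an event for the first window, whatever happens afterwards. The second window contains no such period, so the time and interaction terms compare unlike periods. Section F also does not say that study CBT is left out of the count.

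At stake is whether the result can be read as an effect on aftercare, and possibly some loss of power. The primary endpoint is not involved.

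**Working it through.** **Inputs.** Day 0 is session 1, which is randomisation (D.3). Sessions are weekly (D.4.1), so session k falls on day 7(k − 1). The quit date is session 3 (D.4.2), day 14. Study treatment ends on day 77 (session 12) or day 84 (12 full weeks). Take six months as M = 182 days.

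**Check of the plan's own timeline.** Section D.4.2 says that starting at session 3 "which will provide eight weeks of mCM before the end of CBT", and that "Patients who attend all weekly appointments will have two sessions of CBT occurring after mCM ends". On this calendar mCM ends on day 14 + 56 = 70. Sessions 11 (day 70) and 12 (day 77) fall on or after that. Both statements are reproduced.

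**Boundary.** Window 1 runs from day 0 to day 182. The incentive visit is on day 14 + 182 = 196, and the 12-month visit on day 14 + 364 = 378. Days 182–196 lie between the end of window 1 and the incentive visit. Where they go depends on how the second six months is read:

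| Reading of the second six months | Window 2 (days) | Days 182–196 |
|---|---|---|
| Six months counted back from the 12-month visit | 196–378 | In neither window |
| Months 6 to 12 after randomisation | 182–364 | Counted as after the incentive; window ends 14 days before the 12-month visit |
| End of window 1 to the 12-month visit | 182–378 | Counted as after the incentive; window is 196 days long |

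Each reading misplaces or omits the same 14 days. They are 14/(196 − 77) = 12% to 14/(196 − 84) = 12.5% of the time from end of treatment to the incentive visit. If session 3 and the quit date slip, the mismatch widens.

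**Overlap.** Study treatment takes 77/182 = 42% to 84/182 = 46% of window 1. That leaves 182 − 84 = 98 to 182 − 77 = 105 days in which aftercare is encouraged. With M = 180 the shares are 43% and 47%.

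**What the overlap could do.** Suppose a share b of both incentive groups enrols during treatment, independently of later use. A later rate p is then recorded as b + (1 − b)p, and the group difference shrinks by the factor (1 − b). The documents give neither b nor the later rates. As an illustration only, assume later rates of 30% and 50%, 70 per incentive group (140/2), a two-sided 5% test, and no allowance for the repeated measures:

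| b | Recorded rates | Difference | Power |
|---|---|---|---|
| 0% | 30% v 50% | 20 points | 68% |
| 5% | 33.5% v 52.5% | 19 points | 62% |
| 10% | 37% v 55% | 18 points | 57% |
| 20% | 44% v 60% | 16 points | 47% |

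If nobody enrols during treatment (b = 0), the overlap costs nothing.

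**Length of realigned windows.** From the end of treatment to the 6-month visit is 196 − 84 = 112 to 196 − 77 = 119 days, or 16–17 weeks. The second window is six months, and there is no gap.

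**The case against.** The case for leaving the windows alone has real content. The incentive is allocated at session 1, so counting from there is a proper intention-to-treat choice. It gives everyone a fixed window that VA records can fill whether or not they attend. Section D.1 describes Aim 3's outcome as aftercare together with other treatment for alcohol, and the aim itself speaks of treatment utilisation, so a broad count is not contrary to the plan. Early enrolments may be few: people already in professional behavioural treatment for AUD are excluded (D.2), and starting new treatment is discouraged. Section F's power paragraph also places the 6-month point after randomisation, which suggests loose wording more than a deliberate choice.

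Most of this stands. It argues for keeping the count from randomisation, and it limits the size of the problem. It does not make that count a measure of the aftercare in Hypothesis 3, nor does it move the boundary to the incentive visit.

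A reader might infer more than the documents support:

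- **That two weeks of data are lost.** This follows from only one of the three readings.
- **That the comparison is biased.** The request not to start treatment applies alike in both incentive groups. It sits in the mCM subsection but is worded for participants in general.
- **That 42–46% of the effect is diluted away.** That figure is a share of time, not of events.
- **That early enrolments come mainly from people leaving CBT, or that the two weeks are when the incentive acts most strongly.** Neither has a source. The $300 rewards abstinence from heavy drinking, not aftercare, and nothing says when an effect on enrolment would peak.

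**Conclusion.** The point holds as a mismatch between the stated contrast and the windows that are to measure it. With sessions on schedule, the boundary precedes the incentive visit by 14 days on any reading that starts window 1 at randomisation. Study treatment fills 42–46% of that window, and enrolments in that time are not the aftercare named in Hypothesis 3. These figures rest on weekly sessions kept on schedule and a six-month period of about 182 days.

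The consequence is mainly for interpretation. The randomised comparison is not biased by this alone. Dilution may be anything from none upwards, because the number enrolling during treatment is unknown; the power figures above are illustrations on assumed rates. Aim 3 is exploratory and the primary endpoint is unaffected. The change is worth making because it is nearly free.

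**What to change.** In Section F, for the aftercare hypothesis:

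1. Define window 1 as the scheduled end of the 12-week treatment period to the scheduled 6-month visit (timed from the quit date), and window 2 as the following day to the scheduled 12-month visit.
2. Use scheduled dates, including a scheduled quit date for anyone who does not reach session 3, so that every randomised participant has defined windows. Actual visit dates would not serve: Section F's own attrition scenario has 101 of 140 at 6 months and 86 at 12 months, leaving 39 and 54 people without one.
3. State that study CBT is not counted.
4. Keep the count from randomisation as a secondary outcome covering the broader alcohol treatment mentioned in Section D.1, and report enrolment during study treatment separately by incentive group.
5. Reconcile the 6-month anchor in the power paragraph with the quit-date anchor used in Sections D.4.3 and D.8.

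The cost is SAP wording. Table 3 already collects utilisation at post-treatment, 6 months and 12 months, which suits these windows. There are two drawbacks. The first window shortens to about 16–17 weeks and may hold fewer events. Self-reported non-VA use must also be attributable to the new intervals; the documents do not say that the self-report measure records dates, so this should be confirmed.
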